Any participant who receives at least one dose of CAB LA and/or RPV LA and discontinues the CAB LA + RPV LA regimen for any reason before CAB LA + RPV LA marketed product is locally available must enter the 52-week LTFU Phase. Where the CAB LA+ RPV LA marketed product is locally available, only the participants that discontinue the CAB LA+RPV LA regimen for safety-related reasons must enter the 52-week LTFU Phase. Those participants must remain on suppressive highly active antiretroviral therapy (HAAPT) for at least 52 weeks after the last does of CAPIA and/or PPVIA

(HAART) for at least 52 weeks after the last dose of CAB LA and/or RPV LA.

There are two arms for the providers (arm-e and arm-s) which contain different levels and type of support for the implementation of the HIV Regimen. Different implementation components are found in Table 3. Cluster randomization will be used to randomize sites in each country to either arm-e or arm-s.

Table 3 Implementation Components

	Implementation Component	Arm-e	Arm-s
1	Study Treatment Injection Training	Face-to-face	Virtual
2	Toolkits	Х	Х
3	SWAT Meeting	Х	
4	CQI Meetings (once monthly)	Х	

Schema:

OLI = Oral Lead In, M=Month CAB = Cabotegravir, RPV = Rilpivirine, CQI = Continuous Quality Improvement; BL = Baseline, SWAT=Skilled Wrap Around Team; CQI= Continuous Quality Improvement; SDM= Study Delivery Meeting; MSL= Medical Science Liaison

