4.3.4. LTFU Phase – Following the IM Regimen Only

Any participant who receives *at least one* dose of CAB LA and/or RPV LA and discontinues the CAB LA + RPV LA regimen for any reason before CAB LA + RPV LA marketed product is locally available must enter the LTFU Phase. Participants must remain on suppressive HAART for at least 52 weeks after the last dose of CAB LA and/or RPV LA in order to prevent selective pressure on HIV during the period of declining drug exposures and the potential for selection of resistant mutants.

• Where the CAB LA + RPV LA Marketed Product is Locally Available

Only the participants that discontinue the CAB LA + RPV LA regimen for **safety-related reasons** included in Section 7, must enter the LTFU Phase. Participants must remain on suppressive highly active antiretroviral therapy (HAART) for at least 52 weeks after the last dose of CAB LA and/or RPV LA in order to prevent selective pressure on HIV during the period of declining drug exposures and the potential for selection of resistant mutants.

NOTE: Participants who transition to CAB+RPV LA, marketed product or alternative HAART (except due to safety-related reasons) do not need to enter the LTFU Phase.

Investigators must discuss the choice of the follow-up HAART regimen with the Medical Monitor prior to initiating the new regimen with the participant. HAART therapy should be initiated within one month (- 7 days) after the last dose if interruption is prior to Dose 2 and within 2 months (± 7 days) after the last injection if interruption is following Dose 2, however if withdrawn due to virologic failure, HAART should be initiated as soon as virologic failure is confirmed. Discuss with Medical Monitor. The Long-Term Follow Up period (LTFU) will begin the day of the last CAB LA and/or RPV LA dose and continue for 52 weeks.

Marketed product locally available	Subject WD due to safety- related reasons	LTFU phase required?
No	Yes No	Yes
Yes	Yes	Yes
	No	No, but Safety FU visit required to assess potential safety issues occurred after the last injection see Section 4.5.1.2 Safety Follow-up Visit.

Long term Follow up phase requirement

Participants entering the LTFU phase will not complete a Withdrawal visit but will instead move directly into the LTFU Phase as per the schedule of activities. In addition, for participants who withdraw during the LTFU Phase, the final visit will be considered the study withdrawal visit.

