4.5.1.2. Patient Study Participants

The investigator is responsible for ensuring that consideration has been given to the poststudy care of the patient study participant's medical condition.

Patient study participants are considered to have completed the study if they have completed all study visits and assessments up to and including Dose 7 (Month 12).

Post Dose 7 (Month 12), they should remain on study (Extension Phase) until; Commercial supplies of the CAB LA + RPV LA regimen become locally available, they are required to initiate alternate antiretroviral therapy at the discretion of their HIV care provider, or until development of CAB LA + RPV LA is terminated.

Until meeting the definition for study completion, participants will continue in the study until the participant no longer derives clinical benefit or the participant meets a protocoldefined reason for discontinuation.

Following commercial availability, patient study participants will exit the study and transition to commercial supplies of CAB LA + RPV LA, or alternate antiretroviral therapy at the discretion of their HIV care provider.

Safety Follow-up Visit

A safety follow-up visit is required for subjects completing the study when commercial supplies become available, (participant may or may not be transitioning to CAB + RPV LA marketed product). It should be conducted approximately 2-4 weeks after the last dose of IP to assess HIV associated conditions, AEs, Concomitant medications, ISR AEs after the last injection and the plan to transition to marketed product. This visit may be conducted by telephone. Ensure relevant eCRF forms (including the Study Conclusion form) are updated / completed.

Participants who withdraw from CAB LA + RPV LA and go into the LTFU phase will be considered to have prematurely withdrawn from the study intervention.

Follow-Up visits are not required for successful completion of the study.

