7.1.8.3. Confirmed Virologic Failure

Participants with CVF must be discontinued from study treatment. However, participants who have received at least one dose of CAB LA or RPV LA prior to confirming virologic failure will remain in the study on oral HAART in the LTFU Phase.

A plasma sample from the suspected virologic failure visit as well as Day 1 (if baseline HIV-1 RNA level ≥ 200 c/mL) will be sent for genotypic and phenotypic resistance testing and the result made known to the Investigator when available. Baseline proviral genotyping on Day 1 PBMCs and other genotyping techniques may also be attempted for patient study participants with CVF. A plasma sample from the confirmation visit will be obtained for storage. This sample may be used for possible future analyses, e.g., for genotypic and phenotypic analyses etc.

For all participants who meet CVF, baseline and suspected virologic failure plasma samples with HIV-1 RNA level \geq 200 c/mL will be analyzed in an attempt to obtain genotype/phenotype data on as many samples as possible. Plasma samples for storage will also be obtained at unscheduled visits including confirmation of CVF. Participants may continue to receive study drug at the discretion of the Investigator until results of resistance testing are available at which time the participant must be discontinued from the study. Even if genotype/phenotype data cannot be generated, participant must be discontinued from the study intervention.

If a participant is prematurely discontinued from the study intervention, the Investigator must make every effort to perform the Withdrawal Visit evaluations outlined in the Schedule of Activities Table. These data will be recorded as they comprise essential evaluations needed to be done before discharging any participant from the study.

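### After confirmed virologic failure, Protocol Section 7.1.8.3 lets study drug continue until resistance results, against the rule to start HAART at confirmation, and does not bar another injection

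*Protocol*

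**What the plan says.** Section 7.1.8.3 of the Protocol gives these instructions for CVF, which Section 7.1.7 defines as two consecutive HIV-1 RNA results of at least 200 c/mL:

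- It opens with a stop rule: "Participants with CVF must be discontinued from study treatment".
- Participants who have had at least one LA dose "will remain in the study on oral HAART in the LTFU Phase".
- Two paragraphs later, in text covering everyone who meets CVF, the investigator may choose to keep study drug going "until results of resistance testing are available at which time the participant must be discontinued from the study".
- The next sentence uses a different term: "Even if genotype/phenotype data cannot be generated, participant must be discontinued from the study intervention".
- The section ends by asking for the Withdrawal Visit evaluations whenever study intervention stops early.

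Section 4.3.4 sets the HAART timing: "if withdrawn due to virologic failure, HAART should be initiated as soon as virologic failure is confirmed". It then refers the site to the Medical Monitor. The treatment-failure row of the risk table in Section 2.3.2 says that participants with CVF come off study drugs and move to oral HAART. Section 7 lists the virologic criteria among the reasons for which stopping study intervention is mandatory.

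**The concern.** The permission to continue leaves a site with two instructions for the same patient on the same day. One is to stop and start HAART now. The other is that study drug may go on until a laboratory report of unstated timing arrives. With a tablet, the difference would be some further days of dosing. Here study drug may be an intramuscular injection, and Section 6.5.3 says both LA drugs may be measurable in plasma for more than a year. A dose given in the interval would commit a participant with confirmed failure to prolonged further exposure to the failing regimen. The text sets no time limit and does not say whether an injection is allowed.

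The stake is patient management and the risk of resistance, not the trial's statistical conclusions.

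**Working it through.** No figure in the plan needs reproducing. The check sets the instructions side by side and then sizes the group.

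**Study drug and HAART timing**

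1. Opening sentence of 7.1.8.3: stop study treatment at CVF, with no delay mentioned.
2. Section 4.3.4: for other discontinuations HAART may wait, up to one month (−7 days) after the last dose before Dose 2, or two months (±7 days) after the last injection thereafter. Virologic failure is then singled out from those windows, with HAART at confirmation. The trigger is the confirmed viral load, not the resistance report.
3. Section 2.3.2 risk table: off study drugs and on to oral HAART, again without a wait.
4. Later sentence of 7.1.8.3: study drug may continue at the investigator's discretion until the resistance report.

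Items 1 to 3 agree and item 4 departs from them. Reading item 4 as a grace period before the mandatory stop reconciles it with item 1, but not with item 2. Item 4 also does not say whether the drug received in the interval may be an injection. The documents give no turnaround time for resistance testing, so how often an injection would fall due in the interval cannot be worked out.

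**Study status**

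Section 7.1.8.3 keeps LA-exposed participants in the study and also says they leave it. Section 7.2 treats leaving the study as leaving both the intervention and the study, so taken literally the statements conflict. The intended meaning can be recovered: the adjoining sentence says *study intervention*, and Section 4.5.1.2 says that those who "go into the LTFU phase will be considered to have prematurely withdrawn from the study intervention".

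**LTFU and local availability**

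Section 4.1 says that any LA-exposed participant who "discontinues the CAB LA + RPV LA regimen for any reason before CAB LA + RPV LA marketed product is locally available must enter" LTFU. Once the product is marketed locally, Sections 4.1, 4.3.4 and 7.1 require LTFU only for safety-related discontinuations. Section 4.3.4 points to Section 7 for those reasons, but Section 7 does not mark which of its listed reasons are safety-related, so the status of CVF is not stated. Section 7.1.8.3 is unconditional. The gap is not hypothetical: Section 4.2.6.4 expects study start in Germany to overlap with local availability.

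**Withdrawal Visit**

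Section 7.1.8.3 asks for these evaluations after early discontinuation of study intervention. Section 4.3.4 says participants entering LTFU skip the visit, and footnote m of the Schedule of Activities restricts it to those not entering LTFU.

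**Size**

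Section 9.2 gives 474 enrolled and 450 evaluable patients. No CVF rate is stated, so assume 0.5% to 2%:

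- 450 × 0.005 = 2.25; 450 × 0.02 = 9.0
- 474 × 0.005 = 2.37; 474 × 0.02 = 9.48

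Either base gives about 2 to 9 participants. The LTFU points apply only to those who have had an LA dose.

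**The case against.** The best defence is that 7.1.8.3 describes a mandatory stop with a short, bounded delay, and that the delay has a purpose: Section 8.10.1 says resistance results are reported to guide the choice of the next regimen. Footnote v requires the Medical Monitor to be consulted on HAART choice and timing, and Section 7.1.8.2 sends treatment interruptions in virologic failure to the study team. These safeguards reduce the risk. They do not settle which text governs, because the sentence in 7.1.8.3 leaves the decision to the investigator and 4.3.4 keys HAART to confirmation.

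A reader might infer something stronger: that the section ends follow-up for LA-exposed participants with CVF, so that the resistance monitoring described in Section 7.1.8 is lost. The documents do not support that. The section carries its own LTFU rule for LA-exposed participants. Elsewhere the protocol routinely pairs leaving the study with entering LTFU, in Sections 1.1 and 4.3.3 (if IM dosing is stopped programme-wide), in Section 7, and in the diarrhoea and CPK guidance of 10.6.5.2 and 10.6.5.4. A site would have to ignore the section's first paragraph to end LTFU. The study-status clash is a slip of terminology, and the Withdrawal Visit clash is already answered by 4.3.4 and footnote m. Both are worth tidying, but neither would justify the point alone.

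**Conclusion.** The conflict on study drug and HAART timing stands. Section 7.1.8.3 contradicts its own opening sentence, Section 4.3.4 and the Section 2.3.2 risk table, and leaves open a further irreversible injection after confirmed failure. The wording on study status and the Withdrawal Visit is a secondary inconsistency whose intended meaning is clear. Whether CVF requires LTFU after local availability is a real gap.

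The effect is small in numbers: about 2 to 9 participants, resting wholly on the assumed 0.5% to 2% CVF rate. It would also be wrong to infer damage to the trial's results. CVF is fixed by the second viral load, before the disputed interval begins. Resistance testing uses plasma from the suspected-failure visit, which has already been drawn. The primary endpoint is the staff AIM/IAM/FIM scores. The correction is worth making because it is cheap and bears on the safety of patients already failing treatment.

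**What to change.** In Section 7.1.8.3:

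1. Replace the permission to continue with a statement that no further CAB LA + RPV LA injection is given once CVF is confirmed, and that HAART starts as Section 4.3.4 directs, in consultation with the Medical Monitor.
2. Change the study-status wording so that the participant is discontinued from the study intervention and, if LA-exposed, enters LTFU regardless of local product availability. Align Sections 4.1, 4.3.4 (including its table) and 7.1 so that CVF requires LTFU after local availability too. The Synopsis and Section 7 repeat the safety-only rule and need the same change.
3. Limit the Withdrawal Visit sentence to participants not entering LTFU.

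The cost is a few sentences of protocol text and no change to the SAP analyses. Any participant with CVF newly brought into LTFU after local availability would have up to four clinic visits (months 3, 6, 9 and 12). The real loss is a short investigator discretion to wait for resistance results before choosing a regimen. Those results would still inform the regimen when they arrive. If the sponsor prefers to keep the discretion, the text should give it a time limit, state that it does not extend to an injection, and amend Section 4.3.4 to match.

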7.2. Participant Discontinuation/Withdrawal from the Study

• A participant may withdraw from the study at any time at his/her own request or may be withdrawn at any time at the discretion of the Investigator for safety,

behavioral, compliance or administrative reasons. This is expected to be uncommon.

- At the time of discontinuing from the study, if possible, an early withdrawal visit should be conducted, as shown in the SoA (see SoA for data to be collected at the time of study discontinuation and follow-up and for any further evaluations that need to be completed).
- The participant will be permanently discontinued both from the study intervention and from the study at that time.
- If the participant withdraws consent for disclosure of data for further research, the sponsor may retain and continue to use any data collected before such a withdrawal of consent for the study primary research but data will not be used for further research.
- If a participant withdraws from the study, he/she may request destruction of any samples taken and not tested, and the Investigator must document this in the site study records.

7.3. Lost to Follow Up

A participant will be considered lost to follow-up if he or she repeatedly fails to return for scheduled visits and is unable to be contacted by the study site.

The following actions must be taken if a participant fails to return to the clinic for a required study visit:

- The site must attempt to contact the participant and reschedule the missed visit as soon as possible and counsel the participant on the importance of maintaining the assigned visit schedule and ascertain whether the participant wishes to and/or should continue in the study.
- Before a participant is deemed lost to follow up, the Investigator or designee must make every effort to regain contact with the participant (where possible, 3 telephone calls and, if necessary, a certified letter to the participant's last known mailing address or local equivalent methods). These contact attempts should be documented in the participant's medical record.
- Should the participant continue to be unreachable, he/she will be considered to have withdrawn from the study.

Discontinuation of specific sites or of the study are handled as part of Section 10.1.

8. STUDY ASSESSMENTS AND PROCEDURES

Protocol waivers or exemptions are not allowed except for urgent actions to address immediate safety concerns. Therefore, adherence to the study design requirements, including those specified in the Schedule of Activities Table, are essential and required for study conduct.

This section lists the procedures and parameters of each planned study assessment. The exact timing of each assessment is listed in the Schedule of Activities, Section 1.3.

Laboratory results from the central laboratory services provided by this trial will be used to assess eligibility and scheduled assessments. The use of local laboratory services to assess eligibility is only allowed with prior approval (before to initiating the study) obtained by the study team with agreed guidance.

The following points must be noted:

If assessments are scheduled for the same nominal time, THEN the assessments should occur in the following order:

- 1. vital signs
- 2. blood draws

•The IRB/independent ethics committee (IEC) will be informed of any safety issues that require alteration of the safety monitoring scheme or amendment of the Informed Consent Form.

8.1. Screening Assessments

Eligibility criteria must be carefully assessed at the Screening visit. Physical examinations should be conducted as part of normal routine clinical care. Background information to be collected at Screening includes demography and prior ART history.

Eligible participants may be enrolled immediately as soon as all Screening assessments are complete, and the results are available and documented. All participants will complete the screening period of approximately 35 days prior to Oral Lead-in during which all clinical and laboratory assessments of eligibility must be performed and reviewed. All Screening results **must** be available prior to enrollment.

All information about the participant's current regimen must be available for review by the Principal Investigator or designee prior to enrollment. Source documents from other medical facilities must be located/received during the 35-day screening period and under no circumstances may the participant be enrolled in the absence of source documentation even if there are delays in receipt of this information.

Participants who meet all entry criteria and are enrolled will be assigned a participant number. A single repeat of a procedure/lab parameter can determine eligibility (unless otherwise specified). Participants not meeting all inclusion and exclusion criteria at initial screen may be rescreened one time within 4 weeks and receive a new participant number. Participants who are enrolled into the trial and subsequently withdrawn from the study for any reason may not be rescreened.

8.2. Baseline Assessments

8.2.1. Patient Study Participants

At Day 1, any changes to the eligibility parameters must be assessed and any results required prior to enrollment (e.g., Day 1 urine pregnancy test for women of childbearing potential) must be available and reviewed. The following demographic parameters will be captured: year of birth, sex, race and ethnicity. Medical/medication/family history will be assessed as related to the inclusion/exclusion criteria listed in Section 5.1.

Baseline information to be collected at Day 1 includes general medical history and current medical conditions. Laboratory assessments will also be assessed. Questionnaire are recommended to be administered at the beginning of the visit before any other assessments are conducted, in the order specified.

In addition to a full routine medical history at Baseline, more detailed information will be collected for some disease processes such as:

- Cardiovascular medical history/risk factors (as detailed in the eCRF) will be assessed at Baseline and assessments will include height, weight, blood pressure, smoking status and history, pertinent medical conditions (e.g., hypertension, diabetes mellitus), and family history of premature cardiovascular disease. In addition, medical history/risk factors for renal disease such as nephropathy, renal failure, and nephrolithiasis will be assessed.
- history of illicit drug use [e.g., cocaine, heroin, and methamphetamine use]);
- intravenous drug use history;
- gastrointestinal disease (e.g., gastrointestinal [GI] bleeding, peptic ulcer disease [PUD], etc);
- metabolic (e.g., Type I or II diabetes mellitus);
- psychiatric (e.g., depression);
- renal (e.g., nephrolithiasis, nephropathy, renal failure); and,
- neurologic disorders

Procedures conducted as part of the participant's routine clinical management [e.g., laboratory assessments] and obtained prior to signing of informed consent may be utilized for baseline purposes provided the procedure meets the protocol-defined criteria and has been performed in the timeframe of the study. Where possible local lab results should be confirmed by submission of samples to the central lab.

8.2.2. Staff Study Participants

Questionnaires and Interviews for staff study participants should be completed prior to the first Patient Study Participant CAB LA + RPV LA injection.

8.3. Efficacy Assessments- Patient Study Participants

8.3.1. Plasma HIV-1 RNA

Plasma for quantitative HIV-1 RNA will be collected according to the Schedule of Activities (Section 1.3). Methods to be used may include but are not limited to the Abbott RealTime HIV-1 Assay lower limit of detection (LLOD) 40 c/mL. In some cases, (e.g., where the HIV-1 RNA is below the lower limit of detection for a given assay) additional exploratory methods may be used to further characterize HIV-1 RNA levels.

